19.9 Detailed Surgical Planning

All Patients will have pre-operative CT scan for planning as per current standard technique.

Prior to surgery Patient's pre-operative plan will be formulated on the basis of their randomisation.

The **control group** will be planned to mechanical axis alignment.

To do this the tibia will be sized to best match with the tibial plateau size without more than 2mm overhang anterolaterally or posteriorly and no overhanging of cortices medial and laterally. The coronal angulation of the tibia will be 0° of varus/valgus and posterior slope will be 3°. Resection depth will be set to a depth of 7mm maximal resection.

The femur will initially be planned with the same size as the tibia and 8mm resection depths posteriorly and distally. Coronal angulation will be zero degrees varus/valgus and flexion of 3° for males and 5° for females. Size is then adjusted to allow best match to condylar radius of curvature. Femoral rotation will be set to parallel to surgical epicondylar axis. Femoral flexion angle is then altered within the range of 0-7° to optimise the anterior cut exit point. If unable to accommodate size without notching anterior cortex or having the tip of the implant achieving bony contact, size will be altered to achieve this. Medial lateral width of component will not overhang distal femur or will be downsized.

The **investigation group** will be planned with Kinematic Axis alignment. This will be changed to functional alignment intra-operatively once soft tissue balance assessed.

To achieve this the tibia will be sized to best match with the tibial plateau size without more than 2mm overhang anterolaterally or posteriorly and no overhanging of cortices medial and laterally. The resection depths will be set to 7mm medially and laterally. (N.B. This may exceed 6° of varus angulation but this will be adjusted intra-operatively).

The same size femur is then used as starting size. 6.5mm resections are planned medially and laterally from the distal and posterior condyles. (N.B. this may result in excessive valgus but this will be adjusted intra-operatively). Femoral flexion angle is then altered within the range of 0-7° to optimise the anterior cut exit point. If unable to accommodate size without notching anterior cortex or having the tip of the implant achieving bony contact size will be altered to achieve this. Medial lateral width of component will not overhang distal femur or will be downsized.

Tibial slope is then matched to native slope whilst not exceeding combined femoral flexion and tibial slope of more than 10°. If this value exceeds 10° then tibial slope is reduced.

A standard anaesthetic approach involving Spinal anaesthetic involving 2.5mls of heavy bupivacaine and 30-60mcg buprenorphine (dependant on patient size and comorbidities). An Adductor block is then performed with ultrasound guidance using bupivacaine. Sedation or GA is then undertaken as per patient preference for comfort and anxiety. If the anaesthetic is required to be altered for any reason it will be done so at the discretion of the Consultant Anaesthetist in the best interests of the patient and any variation will be recorded.

Surgical approach is consistent for both groups. Following Anaesthetic and IDC insertion a pre-prep is undertaken with alcohol based skin prep. A tourniquet is then applied and inflated to 300mm Hg immediately prior to skin preparation and draping. The surgical area is then protected with an iodine occlusive dressing (Ioban).

The incision is midline with a medial parapatellar approach. Trackers and checkpoints are inserted into the femur and tibia, The ACL is resected if present.

Registration is then undertaken. Osteophytes are then removed from distal femur and medial tibia. A pre-resection

balancing workflow is then undertaken with maximal soft tissue gaps measured at 10 degrees of flexion and 90 degrees of flexion.

This results in the following table which values are the used as per below treatment algorithms to balance TKA

	Medial maximal gap(mm)	Lateral maximal gap(mm)
Extension	**	**
Flexion	**	**

The aim is to balance the knee within the alignment principles of each treatment arm such that extension is balanced from medial to lateral to within 1mm (2mm acceptable) and balanced from extension to flexion on the medial side to within 1mm (2 mm acceptable). The lateral flexion gap is allowed to be lax with the resections described above. The lateral flexion gap should not be tighter than the medial flexion gap.

For the **Control Group** (MA alignment) the following is undertaken to balance the TKA

These steps are undertaken but will always observe limits in below table

Parameter	Limit
HKA	2° varus – 2° valgus
Tibial coronal	2° varus – 2° valgus
Tibial slope	0°-3° posterior slope
Femoral coronal	2° varus – 2° valgus
Femoral rotation	0° IR to 3° ER to SEA
Femoral flexion	0°-7° flexion
Combined flexion (tibial slope + femoral flexion)	Max 10°

STEP 1

Alter tibial resection depth until maximal extension gap is 20mm

STEP 2

Balance the extension gap as per table below

Gap measurements	Action
Lateral ext = 20mm Medial ext <20mm	Increase Tibial varus up to two degrees with COR locked on LTP
Lateral = 20mm Medial = 20mm	Move on to Flexion balance
Lateral < 20mm Medial = 20mm	Increase Femoral valgus up to two degrees with COR locked on MFC

The medial or lateral side may remain tight after these steps. This indicates the need for soft tissue release. These will be undertaken at the trial phase where the soft tissues will be under tension and release is easier to perform.

STEP 3

Balance Medial flexion gap as per table below. N.B. If medial extension gap remains tight aim to match medial flexion gap to equalise medial side

Gap measurements	Action
Medial Flex = Medial Ext Lateral flex >=20mm	Move on to check Femoral flexion
Medial flex < Medial extension Lateral flex >= 20mm	Externally rotate femur by up to 3 degrees with COR locked on posterior lateral femoral condyle
Medial flex < Medial extension Lateral flex < 20mm	Increase posterior resection depth until medial flexion depth equals medial extension gap. (N.B. need to check femoral rotation allows for sufficient bone contact anteriorly)
Medial flex > Medial extension Lateral flex > 20mm	Decrease posterior resection depth until medial flexion depth equals medial extension gap. (N.B. need to check femoral rotation prevents notching anteriorly)
Medial Flex = Medial Ext Lateral flex < 20mm	Requires internal rotation of femur with COR locked on posterior medial femoral condyle (N.B. Surgeon required to check stability of femoral tracker in flexion with the checkpoint as this may cause this rare combination)

STEP 4

Check Anterior cut on plan to ensure enough bone contact without notching. Anterior cut should exit within 1cm of tip of femoral prosthesis. Femoral flexion with COR locked at centre of femoral component radius of curvature should be adjusted within the range 0-7 degrees of flexion to finalise component position.

STEP 5

Execute bone cuts as planned and trial with 9mm insert. Perform soft tissue releases as necessary to balance gaps within 1mm. Utilise ligament balancing page on Mako software to assess soft tissue balance aim for equal gaps and accept differences of up to 2mm if best efforts to balance have been made. Assess sagittal stability clinically and upsize insert if positive drawer test. Partial PCL release can be performed for sagittal balance if tight. This can then be trialled and if adequate sagittal stability a CS insert utilised. IF PCL needs to be completely released for balance then conversion to a PS component will be required.

STEP 6

Insert definitive implants. Tibia and Patella are cemented. The femoral component is uncemented. Reassess balance for final measurements.

STEP 7

Lavage of joint with pulsatile lavage system. LA infiltration with 80-100ml(dependant on patient mass) of 0.2% Bupivacaine, 1g tranexamic acid and 1 ml 1:1000 Adrenaline throughout capsule and soft tissues. Closed in layers with either subcuticular sutures or staples dependant on patient skin quality.

For the **Investigation Group** (Functional alignment) the following is undertaken to balance the TKA. These steps are undertaken but will always observe limits in below table

Parameter	Limit
HKA	6° varus – 3° valgus
Tibial coronal	6° varus – 3° valgus
Tibial slope	0°-7° posterior slope
Femoral coronal	3° varus – 6° valgus
Femoral rotation	6° IR to 6° ER to SEA
Femoral flexion	0°-7° flexion
Combined flexion (tibial slope + femoral flexion)	Max 10°

STEP 1

Alter tibial resection depth until maximal extension gap is 20mm

STEP 2

Balance the extension gap as per table below

Gap measurements	Action
Lateral ext = 20mm Medial ext <20mm	Increase tibial varus up to 6° with COR locked on LTP. If reach Tibial limit of 6° varus then decrease femoral valgus with COR locked on LFC until balanced or reach HKA limit.
Lateral = 20mm Medial = 20mm	Move on to Flexion balance
Lateral < 20mm Medial = 20mm	Decrease tibial varus with COR locked on MFC until reach HKA limit

The medial or lateral side may remain tight after these steps. This indicates the need for soft tissue release. These will be undertaken at the trial phase where the soft tissues will be under tension and release is easier to perform.

STEP 3

Balance Medial flexion gap as per table below. N.B. If medial extension gap remains tight aim to match medial flexion gap to equalise medial side

Gap measurements	Action
Medial Flex = Medial Ext Lateral flex >=20mm	Move on to check Femoral flexion
Medial flex < Medial extension Lateral flex >= 20mm	Externally rotate femur with COR locked on posterior lateral femoral condyle until balance achieved
Medial flex < Medial extension Lateral flex < 20mm	Increase posterior resection depth until medial flexion depth equals medial extension gap. (N.B. need to check femoral flexion allows for sufficient bone contact anteriorly)

Medial flex > Medial extension Lateral flex > 20mm	Decrease posterior resection depth until medial flexion depth equals medial extension gap. (N.B. need to check femoral rotation prevents notching anteriorly)
Medial Flex = Medial Ext Lateral flex < 20mm	Requires internal rotation of femur with COR locked on posterior medial femoral condyle (N.B. Surgeon required to check stability of femoral tracker in flexion with the checkpoint as this may cause this rare combination)

STEP 4

Check Anterior cut on plan to ensure enough bone contact without notching. Anterior cut should exit within 1cm of tip of femoral prosthesis. Femoral flexion with COR locked at centre of femoral component radius of curvature should be adjusted within the range 0-7 degrees of flexion to finalise component position.

STEP 5

Execute bone cuts as planned and trial with 9mm insert. Utilise ligament balancing page on Mako software to assess soft tissue balance aim for equal gaps and accept differences of up to 1mm. For greater differences adjust plan of tibial cut to balance if possible within specified limits. Perform recut and reassess balance. If unable to achieve balance within limits of bony alignment perform soft tissue releases as necessary to balance gaps within 1mm. Utilise ligament balancing page on Mako software to assess soft tissue balance aim for equal gaps and accept differences of up to 2mm if best efforts to balance have been made. Assess sagittal stability clinically and upsize insert if positive drawer test. Partial PCL release can be performed for sagittal balance if tight. This can then be trialled and if adequate sagittal stability a CS insert utilised. IF PCL needs to be completely released for balance then conversion to a PS component will be required.

STEP 6

Insert definitive implants. Tibia and Patella are cemented. The femoral component is uncemented. Reassess balance for final measurements.

STEP 7

Lavage of joint with pulsatile lavage system. LA infiltration with 80-100ml(dependant on patient mass) of 0.2% Bupivacaine, 1g tranexamic acid and 1 ml 1:1000 Adrenaline throughout capsule and soft tissues. Closed in layers with either subcuticular sutures or staples dependant on patient skin quality.

Post-operative Management

All patients will be transferred to recovery. There they will have standard pain protocol guidelines followed. When alert, comfortable and stable the patient will be transferred back to the orthopaedic ward. Intravenous fluids will continue until drinking oral fluids.

Patients will be charted regular slow release narcotic analgesia and immediate release narcotic to be given as required. Oxycodone will be first choice narcotic with Tapentadol, Buprenorphine, and Tramadol as second line agents.

Patients will also be charted regular Paracetamol, Celebrex (if<80 years and good renal function), Pregabalin (dose dependant on age and size). They will have regular aperients.

All patients will have regular cryotherapy.

IDC will be removed prior to 8am morning after surgery. IV cannula will be removed after last dose of IV Abs (24/24 post surgery).

Patients will be stood and have their knee ranged on day of surgery. They will mobilise as able and no limits will be placed on flexion range.

Patients will have daily Physiotherapy and undertake self-directed exercise three times per day consisting of seated flexion exercises and bed based extension exercises.

Discharge criteria will be patient comfortable and safely mobile utilising oral analgesia, with a dry wound and greater than 80 degrees of flexion, having had a bowel motion.

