2.1 Primary objective

- The primary objective of this study is to compare clinical outcomes at two years following surgery between FA TKA and MA TKA. The primary outcome measure for this study is the Forgotten Joint Score (FJS) at two years after surgery. The null hypothesis is that there is no difference in functional scores at two years following surgery between patients undergoing MA TKA (control group) versus FA TKA (investigation group). The hypothesis is that outcome measures obtained at two years after surgery in patients undergoing FA TKA are not achievable using MA TKA. Further PROMs will be used to further assess clinical outcomes including Forgotten Joint Score (FJS), Oxford Knee Score (OKS), Knee injury and osteoarthritis outcome Junior score (KOOS Jr), VAS Pain, and Kujala scores preoperatively and postoperatively at 3 months, 1 year and 2 years. Also health-related quality of life will be measured using European Quality of Life questionnaire with 5 dimensions for adults (EQ-5D-5L) preoperatively and postoperatively at 3 months, 1 year and 2 years. Range of movement (degrees) in knee joint during inpatient admission and postoperatively at 6 weeks, 3 months, 1 year and 2 years.

2.2 Secondary objectives The secondary objectives of the study are:

- Determine lower limb alignment achieved with both alignment techniques. Lower limb alignment as assessed using standing long leg x-rays performed postoperatively at 3 months. Measurements of the hip-knee-angle (HKA), medial proximal tibial angle (MPTA) and lateral distal femoral angle (LDFA). Also evidence of imbalance with implant lift off will be measured.

- Determine if there are any differences in analgesic requirements based on alignment method used. Analgesia requirements during inpatient admission and postoperatively at 6 weeks, 3 months, 1 year and 2 years will be measured.
- Determine whether alignment method utilized has an effect on the sagittal stability of the TKA. Assessment of sagittal stability at Preop, 3 months, 1 year and 2 years will be undertaken with an arthrometer “Lachmeter”.
- Determine whether alignment method utilized has an effect on functional outcomes. This will be assessed by a combination of
 - Maximum voluntary isometric force using a hand-held dynamometer at Preop, 3 months, 1 year and 2 years.
 - Sit to stand values as measure of function at Preop, 3 months, 1 year and 2 years.

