3.5 Sample Size In total, 100 patients will be enrolled in a 1:1 ratio between the two treatment groups. This will ensure that the minimum of 90 patients required to answer the study question are followed up for the duration of the study. The enrolment goal is to have at least 45 patients in each of the two treatment groups completing the study. Sample size calculation and statistical analysis are more comprehensively detailed in section 6.

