3.8 Description of the device

The Stryker Triathlon (Stryker Navigation, Mahwah, NJ) cruciate retaining knee system with patellar resurfacing will be used in both groups. The femoral component will be un-cemented, patella and tibial components will be cemented. This implant and its surgical instruments are already in routine use for TKA at St John of God Subiaco Hospital. The surgical team are fully trained and experienced with the use of the instruments and surgical equipment for these implants.

All postoperative rehabilitation will follow Perth Hip and Knee Clinic standard practice at St John of God Subiaco Hospital for patients undergoing TKA. This will include a combination of inpatient and outpatient physiotherapy as required. Each patient will have standard radiographic and clinical follow-up. The required outcomes from these clinical and radiological assessments will be recorded in the follow-up investigator form at discharge.

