3.10 Clinical and radiological assessment

The FJS, EQ5D-5L, OKS, VAS Pain, Likert scale, KOOS Jr and Kujala Anterior knee pain scores are validated tools for the clinical assessment of patients after knee arthroplasty (10,11,18,19). Each of these scores is completed preoperatively and then at regular intervals during follow-up (Appendix 19.1). This information is routinely discussed at each of these outpatient consultations but patients in this study will have the information recorded within these validated questionnaires to facilitate data analysis.

Routine clinical measures of height, weight, range of movement and pain description will be taken. To test endurance and strength, a 30 sec Sit to stand test will be measured. This test asks the participant to stand up / sit down from a standardised chair height within 30 seconds (Appendix 19.6). To measure the AP stability of the knee (20), a lachmeter reading will also be recorded at the post operative intervals and to measure strength, a hand

held dynamometer test will also be performed.

	Preoperative	Discharge	6 weeks	3 months	1 year	2 years
Patient demographics	X					
Patient medical history	X					
Operation details		X				
Clinical history and PROMS (FJS, EQ5D-5L, OKS, VAS pain, KOOS Jr, Kujala Anterior Knee Pain, Likert scale)	X		X (FJS and VAS only)	X	X	X
Functional Examination (Lachmeter testing, Range of Movement, Hand Held Dynamometer, 30s STS test)	X	X (range only)	X (range only)	X	X	X
Adverse Events	At occurrences through study period					

Table 1. Timelines for clinical data collection in all study patients.

	Preoperative	Discharge	6 weeks	3 months	1 year	2 years
Plain knee joint radiographs	X	X			X	X
Plain long-leg radiographs	X			X		
CT Knee joint	X					

Table 2. Timelines for radiological data collection in all study patients. Assessment windows will be as followed; 6 weeks review (± 1 week), 3 month review (± 2 weeks), 12 month review (± 2 months), 2 year review (± 2 months).

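### Inpatient range of movement is scheduled only at discharge, which itself requires more than 80 degrees of flexion, so any true inpatient flexion difference between the arms is attenuated by an amount the documents cannot fix

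*Combined protocol and SAP*

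**What the plan says.** Section 2.1 lists among the outcomes "Range of movement (degrees) in knee joint during inpatient admission and postoperatively at 6 weeks, 3 months, 1 year and 2 years". It names no post-operative day for the inpatient value.

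Table 1 in section 3.10 has a row "Functional Examination (Lachmeter testing, Range of Movement, Hand Held Dynamometer, 30s STS test"). Its only inpatient column after surgery is Discharge, marked for range only. Section 3.8 agrees: "The required outcomes from these clinical and radiological assessments will be recorded in the follow-up investigator form at discharge". The visit windows printed under Table 2 begin at 6 weeks, so discharge is tied to no post-operative day.

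Section 19.9 (Post-operative Management) sets the discharge rule: "Discharge criteria will be patient comfortable and safely mobile utilising oral analgesia, with a dry wound and greater than 80 degrees of flexion", followed by a bowel criterion. It also describes inpatient care: "Patients will be stood and have their knee ranged on day of surgery" and "Patients will have daily Physiotherapy and undertake self-directed exercise three times per day". Neither sentence asks for a recorded ROM value.

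The intra-operative form (Appendix 19.8) has ROM fields, but they describe the anaesthetised knee. The case report forms in Appendix 19.1 run from the preoperative visit to 6 weeks, 3 months, 12 months and 24 months, with no discharge page. Length of stay and time to 80 degrees are not listed as outcomes.

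**The concern.** The time of measurement is set by the variable being measured. A knee that bends well is measured as soon as the other criteria are met, at whatever it has reached. A stiff knee is given more days and is measured only once it has passed 80 degrees. The two values come from different post-operative days, and neither can lie at or below 80 degrees if the rule is followed.

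If one alignment method gives faster early flexion, part of that advantage shows up as earlier discharge instead of a higher discharge reading. The plan does not analyse time to discharge, so that part is lost. At stake is the reading of a small or null difference in discharge ROM: the schedule could produce it even if early flexion differed. Analysis cannot recover a fixed-day value that was never recorded.

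**Working it through.** **Inputs from the documents.** The threshold is more than 80 degrees (section 19.9). Discharge is the only inpatient time point (Table 1). The target is 45 completers per arm (section 3.5), and secondary tests are two-sided at 0.05 (section 6.2.2). The plan states no figure for inpatient ROM, so there is none to reproduce.

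**Inputs that must be assumed.** The documents give no inpatient flexion mean, SD, daily gain or length of stay. All of these are assumptions below, shown over a range.

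**Check 1: a simple floor.** Let X be flexion when the other criteria are met. A patient below 80 waits and is measured on reaching it, so the recorded value is Y = max(X, 80). For X normal with mean μ and SD σ, and a = (80 − μ)/σ:

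E[Y] = 80·Φ(a) + μ·(1 − Φ(a)) + σ·φ(a)

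Take a true difference of 5 degrees and σ = 10.

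- Control, μ = 80, a = 0: 80 × 0.5 + 80 × 0.5 + 10 × 0.3989 = 83.99.
- Comparator, μ = 85, a = −0.5: 80 × 0.3085 + 85 × 0.6915 + 10 × 0.3521 = 86.98.
- Difference at discharge: 86.98 − 83.99 = 2.99, or 60% of 5.

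Over SDs of 10 to 15, the share retained is 23–31% at a control mean of 70, 57–60% at 80, 80–89% at 90, 93–99% at 100 and 98–100% at 110. With 45 per arm and SD 10, power falls from 0.66 to 0.56 at a mean of 80 and stays at 0.66 at a mean of 100.

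**Check 2: recovery day by day.** Day-1 flexion is normal with SD 12 and a true difference of 8 degrees. The daily gain is normal with mean 5 or 8 and SD 3, floored at zero. Discharge is on the first permitted day with flexion above 80 (simulation, 400,000 per arm). Ranges cover the two gains. A fixed day-2 reading shows the full 8 degrees and a standardised effect of 0.65.

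| Control day-1 mean | Difference at discharge, earliest day 2 | Share retained | Standardised effect | Extra stay, slower arm (days) | Share retained, earliest day 4 |
|---|---|---|---|---|---|
| 65 | 1.8–2.1 | 23–27% | 0.37–0.38 | 0.7–1.2 | 52–74% |
| 70 | 2.9–3.4 | 36–42% | 0.47–0.48 | 0.6–1.0 | 67–85% |
| 75 | 4.2–4.6 | 52–58% | 0.54–0.55 | 0.4–0.8 | 80–92% |
| 80 | 5.4–5.8 | 68–73% | 0.59–0.60 | 0.3–0.5 | 89–97% |
| 85 | 6.4–6.8 | 81–85% | 0.62–0.63 | 0.2–0.3 | 94–99% |
| 90 | 7.2–7.4 | 90–93% | 0.64 | 0.1–0.2 | 97–100% |
| 95 | 7.6–7.8 | 95–97% | 0.65 | below 0.1 | 99–100% |

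The standardised effect falls less than the raw difference because the floor also narrows the spread. At a mean of 65 it keeps 0.37/0.65 = 57%, against 23–27% of the raw difference.

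**Check 3: no true difference.** With the same recovery distribution and the same rule in both arms, discharge values have the same distribution, so the expected difference is zero. The floor does not create a difference.

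**The case against.** Four arguments weigh against the point.

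- **Flexion is only one of several discharge conditions.** The list ends "greater than 80 degrees of flexion, having had a bowel motion" and also covers comfort, safe mobility, oral analgesia and a dry wound. If those usually decide the day, the floor seldom binds. This stands: the documents do not say which condition usually binds, and the day-4 column shows how much milder the effect becomes.
- **The error is conservative.** The rule is common to both arms, and section 3.6 keeps the staff who record post-operative outcomes blinded. This also stands: a positive finding at discharge would not be an artefact of the floor.
- **Little depends on it.** ROM is a supporting measure, read again at 6 weeks, 3 months, 1 year and 2 years without this condition. The sample size rests on the FJS. This limits the importance of the point but does not repair the inpatient comparison.
- **A fixed early reading has its own noise.** Section 19.9 uses an adductor block and local infiltration, and a reading soon after surgery reflects these and pain. That is a real cost, but it does not tie the day of measurement to the outcome.

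A reader might infer more than the documents support. The endpoint is not truncated in the strict sense, because stiff patients are measured later and not dropped. Nor is every early difference shrunk: only the flexion end of the inpatient range is constrained. Nor can one say that a null discharge result would be produced by the schedule, since with early flexion well above 80 degrees almost nothing is lost.

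**Conclusion.** The structure and the direction hold on the documents alone. The only scheduled inpatient ROM reading is conditional on exceeding 80 degrees of flexion and falls on a day that depends on recovery. Following the plan attenuates a true inpatient flexion difference and moves part of it into length of stay, which is not analysed.

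The size cannot be derived from the documents. Under the assumptions shown, the share of an 8-degree difference retained runs from about a quarter (day-1 mean 65, earliest discharge day 2) to nearly all. Nearly all means a day-1 mean of 90 or more, or of 85 or more if other criteria delay discharge to day 4. Confidence is therefore high for the mechanism and low for its practical importance. The two-year FJS comparison is not touched. This is a cheap improvement to a supporting outcome, not a threat to the trial's main conclusion.

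**What to change.** 1. In section 2.1 and Table 1, add an inpatient ROM reading at one fixed post-operative physiotherapy session, the same in both arms. Choose a session early enough that no patient has yet gone home. Use this reading for the inpatient comparison.
2. Record the discharge date and the day on which flexion first exceeds 80 degrees.
3. Keep discharge ROM as a descriptive result, reported alongside length of stay.

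The discharge criteria are not changed.

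**Cost.** One added entry in Table 1 and a short inpatient page in Appendix 19.1. Daily physiotherapy is already planned, so no extra visit or staff is needed. The downside is that an early fixed-day reading is more affected by pain and the nerve block.

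The protocol is dated October 2021 and its own milestones end recruitment in December 2021, so the new reading may not exist for patients already operated on. For them, the discharge date and any ROM in the physiotherapy notes could be retrieved if they were recorded. Otherwise, discharge ROM should be reported with this limitation stated.
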